7.4.2 Physical Examination

Physical examinations will be performed at the time points specified in

This document is confidential.

Table 1, Table 2, and Table 3. Findings will be listed.

7.4.3 Vital Signs

Vital signs will be performed at the time points specified in

This document is confidential.

Table 1, Table 2, and Table 3. The actual value and change from baseline to each visit and at end of study will be descriptively summarized by visit/assessment for vital signs (i.e., systolic and diastolic blood pressure, pulse rate, respiratory rate, temperature, and body weight).

Height is measured at screening only. All vital sign data will be reported in a by-patient listing.

7.4.4 Electrocardiogram

A 12-lead electrocardiogram (ECG) will be performed at baseline for patients with a history or symptoms of cardiac or respiratory abnormality 12-lead if not performed within 1 month of study entry.

Electrocardiogram data will be provided in a by-patient listing.

7.4.5 Laboratory Parameters

Safety laboratory assessments will be performed at the time points specified in

This document is confidential.

Table 1, Table 2, and Table 3.

The actual value and change from baseline to each visit and at end of study for each laboratory parameter reported in Table 5 will be descriptively summarized. Shift from baseline to highest CTCAE grade tables for key parameter will also be presented. The number and percentage of patients with any laboratory CTCAE grade increase from baseline and a laboratory CTCAE grade increase from baseline to Grade 3-4 will be summarized.

Laboratory results will be included in by-patient listings.

Table 5 Clinical Laboratory Parameters

Hematology	Chemistry	Urinalysis
Hemoglobin	Albumin	Blood
Total red blood cell count	Alkaline phosphatase	Leukocytes
Total white blood cell (WBC) count	Aspartate aminotransferase	Glucose
absolute values for individual WBC types	Alanine aminotransferase	Ketones
Platelets	Bicarbonate	Nitrites
	Bilirubin	pH
	Blood urea nitrogen	Protein
	Calcium	Specific gravity
	Chloride	Microscopic: WBC, red blood cells, bacteria, epithelial cells, crystals (with type identified), and mucus
	Creatinine	
	Glucose	
	Potassium	
	Sodium	
	Total protein	

7.4.6 Evaluation of Performance Status

The frequency distribution of Eastern Cooperative Oncology Group (ECOG) performance status will be collected at screening and at each study visit in conjunction with the physical examination. ECOG performance assessments will be summarized and listed.

Table 6 Eastern Cooperative Oncology Group Performance Status: Scored 0 (Normal Function) through 5 (Dead)

ECOG PERFORMANCE STATUS^a	
Grade	ECOG
0	Fully active, able to carry on all pre-disease performance without restriction
1	Restricted in physically strenuous activity but ambulatory and able to carry out work of a light or sedentary nature, eg, light housework, office work
2	Ambulatory and capable of all self-care but unable to carry out any work activities. Up and about more than 50% of waking hours
3	Capable of only limited self-care, confined to bed or chair more than 50% of waking hours
4	Completely disabled. Cannot carry on any self-care. Totally confined to bed or chair

This document is confidential.

7.5 Interim Analysis

The first 35 patients in the study are to be CIS patients (with or without papillary disease). An interim analysis for futility will be conducted using the response data in these patients. If 9 or fewer of these first 35 patients achieve CR, the study may be stopped for futility. If 10 or more patients achieve a CR, then the study will continue and all patients meeting entry criteria may be enrolled (including those with papillary disease without CIS). The enrollment will be paused after 35 patients to evaluate this data unless 10 or more responses have already been documented when the 35th CIS patient is enrolled.

When the true CR rate is 40% or higher, the probability of proceeding with 10 or more CRs out of the first 35 patients is over 94%. When the true CR rate is 15% or lower, the probability of 9 or fewer responses is over 97%.

The interim analysis will include summaries of patient disposition, demographics, baseline characteristics, study drug exposure, efficacy and safety data. The summary of efficacy data will include the analysis of the primary endpoint described in Section 7.3.1. This includes a summary of the CR rate, duration of response, and a swim-lane plot. The summary of safety data will include the analyses specified in Section 7.4.1 for TEAEs, treatment-related TEAEs, SAEs, treatment-related SAEs, TEAEs Grade ≥ 3 , and treatment-related TEAEs Grade ≥ 3 by SOC and PT and by PT alone.

The TLF shells of the interim analysis will be provided in the appendix.

7.6 Subgroup Analysis

For efficacy, subgroup analyses will be performed for the CR rate, duration of response, and EFS rate at 48 weeks. The EFS rate at 48 weeks will be based on Kaplan-Meier methods. Subgroup analyses will be performed for the following pre-planned subgroups:

- Tumor staging (CIS alone, CIS with any papillary, HG papillary without CIS [EFS only])
- ECOG 0-1 vs 2
- Recurrence \leq 6 months from last BCG vs $>$ 6 months
- Age (≥ 65 vs < 65)
- Gender
- Race (only if there are more than 10 patients of non-White race)
- BCG unresponsive at most recent recurrence vs. not

Subgroup analyses for the CR rate will be conducted in patients with CIS at baseline, while subgroup analyses for duration of response will be conducted in patients with CIS at baseline with a CR. Subgroup analyses for EFS will be performed for patients in the FAS.

For the key safety analysis (TEAE, treatment-related TEAE, SAE, treatment-related SAE, TEAEs Grade ≥ 3 , and treatment-related TEAEs Grade ≥ 3) the analysis will be performed by below planned subgroups:

- Age (≥ 65 vs < 65)
- Gender

This document is confidential.

- Race

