#### 9.3.1 Inclusion Criteria

Eligible patients must meet the following inclusion criteria:

1. Male or female patients  $\geq 18$  years of age at the time of consent
2. Patient must have been adequately treated with BCG defined as at least one of the following (FDA 2018):
  - a. At least five of six doses of an initial induction course plus at least two of three doses of maintenance therapy
  - b. At least five of six doses of an initial induction course plus at least two of six doses of a second induction course
  - c. A single course of induction BCG can qualify if the patient has T1 high-grade disease at first evaluation (see 3c)
3. Patient must be BCG-unresponsive according to the FDA guidance defined as at least one of the following (FDA 2018):
  - a. Persistent or recurrent CIS alone or with recurrent Ta/T1 disease within 12 months of completion of adequate BCG therapy. An assessment within 15 months can also qualify when no assessment was done 12 months after completion of adequate BCG therapy.
  - b. Recurrent high-grade Ta/T1 disease within 6 months of completion of adequate BCG therapy. An assessment within 9 months can also qualify when no assessment was done 6 months after completion of adequate BCG therapy.
  - c. T1 high-grade disease at the first evaluation following a single course of induction BCG qualifies (Lerner et al. 2015, Steinberg et al. 2016)
4. Patient must have, at study entry, NMIBC indicated by 1 or more of the following:
  - a. Ta or T1 high-grade disease
    - i. No more than 42 days may elapse between the start of protocol therapy and complete resection of Ta/T1 papillary disease qualifying the patient for the study
  - b. CIS disease
    - i. Obvious areas of CIS should be fulgurated prior to start of therapy when indicated
5. Patient must have no known evidence of concomitant upper tract urothelial carcinoma or urothelial carcinoma within the prostatic urethra within 6 months of enrollment
6. Patient must have an Eastern Cooperative Oncology Group (ECOG) performance status  $\leq 2$

7. Patient must have adequate hematologic function, as demonstrated by the following:
  - a. Hemoglobin level  $\geq 10$  g/dL
  - b. Absolute neutrophil count  $\geq 1.5 \times 10^9$ /L
  - c. Platelet count  $\geq 100 \times 10^9$ /L
8. Patient must have adequate liver and renal function as demonstrated by the following:
  - a. Aspartate aminotransferase and alanine aminotransferase each  $\leq 3.0 \times$  upper limit of normal

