7.3.2.1 Event-Free Survival and Time to Recurrence

EFS is defined as the time from first dose of study medication to the first recurrence of disease or death from any cause. Recurrence of disease is defined as

- Appearance of new high-grade disease (ie, new high-grade papillary disease or new CIS) or
- Failure to clear CIS lesions by Week 12 cystoscopy in patients with CIS at baseline

Recurrence must be biopsy proven. Persistence, appearance, or presence of lower grade disease will not be considered recurrence in the primary EFS analyses. Sensitivity analyses will be performed with lower-grade disease also considered an EFS event.

Any patient without tumor in the bladder but presence of urothelial carcinoma in the upper urinary tract or prostatic urethra will not be classified as failures in these analyses and will continue study participation.

Additionally, the overall proportion of patients who have high grade recurrence (and subcategories of persistent CIS, new CIS, new high-grade papillary disease), development of T2 or greater or metastatic disease, cystectomy and death will be summarized for the FAS, and the subgroups with CIS and papillary only disease.

Kaplan-Meier methods will be used to estimate the EFS (ie, percent surviving without a recurrence) and the 95% confidence interval at 12, 24, 36, 48, 72, and 96 weeks in all patients in the FAS and the subgroup of patients with CIS. The median EFS (ie, median time to recurrence) and its 95% confidence interval will also be estimated. Kaplan-Meier plots for EFS will be created.

A sensitivity analysis will also be performed to analyze EFS using binomial methods where patients are considered as being recurrence-free if they have documented recurrence-free survival by the specified time point. Only evaluable patients will be included in the analysis. Patients will be considered evaluable if they have enough follow-up to determine recurrence status at the time point being summarized or if they have discontinued treatment. Exact 95% confidence intervals for EFS will be calculated.

This document is confidential.

A sensitivity analysis for EFS will be performed where if a patient missed a visit and at the next visit he/she experienced a recurrence, the recurrence will be counted from the day of the missed assessment. An additional sensitivity analysis will be performed where recurrence of any NMIBC, including low-grade disease, is counted as an EFS event.

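### The 48-week EFS subgroup by BCG interval is run in the whole FAS, where the entry windows confound the interval with disease type

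*SAP*

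**What the plan says.** SAP 7.6 lists subgroups for the CR rate, the duration of response and the 48-week EFS rate. For EFS, "The EFS rate at 48 weeks will be based on Kaplan-Meier methods". One listed factor is recurrence at most "6 months from last BCG vs" more than 6 months.

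The population differs by endpoint. For CR, "Subgroup analyses for the CR rate will be conducted in patients with CIS at baseline", and duration of response is limited to CIS patients who responded. For EFS, "Subgroup analyses for EFS will be performed for patients in the FAS", so CIS and papillary-only patients are analysed together. SAP 7.6 does not stratify or adjust the interval subgroup by disease type.

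Protocol 9.3.1, criterion 3, sets different windows for the two disease types:

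- 3a, CIS: "Persistent or recurrent CIS alone or with recurrent Ta/T1 disease within 12 months of completion of adequate BCG therapy", extended to 15 months if the 12-month assessment was not done.
- 3b, papillary: "Recurrent high-grade Ta/T1 disease within 6 months of completion of adequate BCG therapy". The extension reads "An assessment within 9 months can also qualify when no assessment was done 6 months after completion of adequate BCG therapy".
- 3c, papillary: high-grade T1 at the first evaluation after one induction course, with no limit in months.

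SAP 7.3.2.1 counts as an EFS event "Failure to clear CIS lesions by Week 12 cystoscopy in patients with CIS at baseline". Papillary disease, by contrast, is completely resected before entry (Protocol 9.1).

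**The concern.** The 6-month cut-point of the subgroup is also the main eligibility limit for papillary disease. A patient beyond 6 months will usually have CIS. A patient at or below 6 months may have either type, and most papillary-only patients should be there.

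Disease type probably matters for EFS because the endpoint works differently in the two types. The planning alternatives for the CR rate in CIS are 35% and 40% (SAP 7.1.5). If CR and CIS clearance roughly coincide, about 60 to 65% of CIS patients would have an EFS event at or soon after Week 12. They do not coincide exactly, so this is only a guide. Papillary-only patients cannot have that event.

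The table could therefore show worse EFS after a longer BCG interval when the interval has no effect, or hide or exaggerate a real effect. Its pre-planned purpose is to describe who benefits, and a reader could easily take such a gap at face value.

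**Working it through.** The documents give no figure for this subgroup, so there is none to reproduce. The check is mixture arithmetic under no true interval effect within either disease type.

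**Inputs from the documents (SAP 7.1.5).** 140 treated patients, of whom 70 to 100 are expected to have CIS. That leaves 140 − 100 = 40 to 140 − 70 = 70 papillary-only patients.

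**Inputs assumed, because the documents give none.**
- Share of CIS patients beyond 6 months: 30% or 50%.
- Share of papillary-only patients at 6 months or less: 100%, then 90%.
- 48-week EFS: 25% in CIS and 45% in papillary-only, a difference D of 20 points. D of 10 (30% and 40%) and 30 (20% and 50%) are also shown.

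**Formula.** With no interval effect, EFS in each interval group is the average of the two disease-type rates weighted by that group's mix. Hence

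gap (short minus long) = (papillary share of short group − papillary share of long group) × D.

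**Case 1: all papillary-only patients at 6 months or less.** The long group is all CIS, with EFS 25%.

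| CIS patients | CIS beyond 6 months | Short group (CIS + papillary) | Papillary share of short group | EFS, short group | Gap |
|---|---|---|---|---|---|
| 70 | 30% | 49 + 70 = 119 | 58.8% | 36.8% | 11.8 points |
| 70 | 50% | 35 + 70 = 105 | 66.7% | 38.3% | 13.3 points |
| 100 | 30% | 70 + 40 = 110 | 36.4% | 32.3% | 7.3 points |
| 100 | 50% | 50 + 40 = 90 | 44.4% | 33.9% | 8.9 points |

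The false gap is about 7 to 13 points. Over the same papillary shares (36 to 67%), D = 10 gives about 4 to 7 points and D = 30 gives about 11 to 20.

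**Case 2: 10% of papillary-only patients beyond 6 months, D = 20.**

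| CIS patients | CIS beyond 6 months | Papillary share, short group | Papillary share, long group | Gap |
|---|---|---|---|---|
| 70 | 30% | 63/112 = 56.2% | 7/28 = 25.0% | 6.2 points |
| 70 | 50% | 63/98 = 64.3% | 7/42 = 16.7% | 9.5 points |
| 100 | 30% | 36/106 = 34.0% | 4/34 = 11.8% | 4.4 points |
| 100 | 50% | 36/86 = 41.9% | 4/54 = 7.4% | 6.9 points |

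The false gap falls to about 4 to 10 points.

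**When it vanishes.** The gap is zero if D = 0, or if the two disease types have the same share of patients at 6 months or less. It changes sign if papillary-only patients have the worse EFS.

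**Within CIS only.** Every patient has the same disease type, so this source of a gap is zero by construction.

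**The case against.** *Much of this is already reported.* Tumor staging, including papillary without CIS, is its own EFS subgroup in SAP 7.6, and SAP 7.3.2.1 gives EFS for CIS patients. CR and duration by interval are CIS-only. The Protocol synopsis also says that analyses will generally be shown by disease type. All of this is true, but the EFS displays are one-way: none crosses interval with disease type, so the interval effect on EFS within CIS cannot be recovered. The general synopsis statement does not displace the explicit FAS rule in SAP 7.6.

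*The size and direction are assumed.* This stands. The documents give neither EFS by disease type nor the distribution of intervals.

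*The table is too imprecise to mislead.* In Case 1 the long group has only 21 to 50 patients. A simple binomial 95% half-width for the difference is about 15 to 20 points, wider than the 7-to-13-point gap. For 50 versus 90 patients it is 1.96 × √(0.25 × 0.75/50 + 0.339 × 0.661/90) = 15.5 points. This limits any firm reading of the table, but it does not remove a bias that the design creates.

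*Stronger readings go too far.* Three are tempting, and the documents support none of them:

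- That the table simply compares CIS with papillary disease. It does not, because CIS patients who recurred early are also in the short group. In Case 1 they are 35/105 = 33% to 70/110 = 64% of it.
- That the entry rules guarantee that nearly all papillary-only patients are at 6 months or less. They do not. There is the 9-month allowance, and the T1 route has no month limit. SAP 7.6 also plans a subgroup of patients who were not BCG-unresponsive at their latest recurrence, so the current recurrence need not be the qualifying one. On the other side, for the same recurrence, counting from the last BCG dose rather than from completion of adequate BCG can only shorten the interval.
- That every other FAS-wide EFS subgroup has the same flaw. No entry rule ties age, gender, ECOG status or race to disease type. Any imbalance there would be chance or case mix, as in any unadjusted subgroup.

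**Conclusion.** The point holds in limited form. The BCG-interval subgroup for 48-week EFS is confounded with disease type by the trial's own entry windows, and SAP 7.6 does nothing to separate the two. It contrasts a mixed group with a mostly-CIS group.

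The size rests on the assumed 20-point EFS difference and the assumed interval split: about 7 to 13 points if all papillary-only patients are at 6 months or less, and about 4 to 10 if 10% are not. The mechanism comes from the documents; the magnitude does not.

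The consequence is modest. This is a descriptive subgroup of a secondary endpoint with no test or decision attached. The primary CR analysis and the CR and duration subgroups are CIS-only and unaffected, as are the interim rule and the main EFS estimates. The change is worth making because it is cheap and removes a known confounder.

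**What to change.** In SAP 7.6, add: *The subgroup analysis of the 48-week EFS rate by BCG interval will be performed in patients with CIS at baseline. The interval is defined as in Section 7.2.5, from the last BCG administration to diagnosis of the current recurrence.* Stratifying this one subgroup by baseline CIS versus papillary-only is an acceptable alternative, although the papillary-only long-interval cell would be nearly empty (4 to 7 patients if 10% of 40 to 70 exceed 6 months).

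Tying the interval to SAP 7.2.5 also settles which recurrence and which BCG date apply, which SAP 7.6 leaves open. It matches the existing CIS-only rule for the CR subgroups. Protocol 13.5.3 leaves further subgroup analyses to the SAP, so the change is one of SAP wording and needs no new data.

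The cost is smaller cells. With 30 to 50% of CIS patients beyond 6 months, the short/long split is 49/21 to 35/35 with 70 CIS patients, and 70/30 to 50/50 with 100. No change to the other EFS subgroups is needed. Splitting them all by disease type would be redundant for tumor staging and would leave very small cells for ECOG 2 and race.

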7.7 Changes to Methods Planned in the Protocol

There are no changes from the analysis planned in the protocol.

This document is confidential.

8. Tables, Listings, And Figures

8.1 Programming Guidelines

Computer-generated output will adhere to the following specifications. The standard operating procedures (SOPs) of Syneos Health Clinical will be followed in the creation and quality control of all tables, listings and figures.

8.1.1 Format of Output

Unless otherwise specified, all computer-generated output should be produced in landscape mode.

Required margins: at least 1.25 inches on top (the binding margin [or left for portrait output]), at least 1 inch on right, left, and bottom. All output should have the Sponsor name, protocol number, the type of delivery, and page number. Tables/listings/figures should be internally paginated in relation to total length (i.e., page number should appear sequentially as page n of N, where N is the total number of pages in the table). All output should have the following header at the top of the page:

Sponsor Name	Confidential	Page n of N
Protocol XXXXXX		

1. Output enumeration will conform to International Conference on Harmonization (ICH) recommendations. The study population should be identified immediately following the title.
2. Column headings should be in initial upper-case characters.
3. For numeric variables, include "unit" in column or row headings where appropriate.
4. Footnotes should be single spaced, but separated by at least a double space from the bottom line of the table. The notes are aligned vertically by the left vertical border of the table.
5. If the categories are not ordered (e.g., race), then only those categories for which there is at least 1 patient represented in 1 or more groups should be included.
6. An Unknown or Missing category should be added to any parameter for which information is not available for 1 or more patients.
7. Listings should be sorted by dose levels and patient numbers.
8. In a listing, display the patient number only once for the patient with multiple records. If a patient's records run into multiple pages, display the patient number once for every page.

8.1.2 Format of Data

1. Unless otherwise specified for continuous variables, the estimated mean, SD and median for a set of values should be printed out to 1 more significant digit than the individual units of measurement. The minimum and maximum should report the same significant digits as the original values.
2. Data in columns of a table should be formatted as follows:
 - Alphanumeric values are left-justified.
 - Whole numbers (e.g., counts) are right-justified.

This document is confidential.

- Numbers containing fractional portions are decimal aligned.

3. Unless otherwise specified, percentage values should be printed with 1 digit to the right of the decimal point (e.g., 12.8%, 5.4%). Less-than signs “<0.1%” should be printed when values are >0.0 and <0.1% (not 0.0%).
4. Missing data should be represented on patient listings as either a hyphen (“-”) with a corresponding footnote (“ - = unknown or not evaluated”), or as “N/A,” with the footnote “N/A = not applicable,” whichever is appropriate.
5. Dates should be printed in SAS ISO 8601 format (“YYYY-MM-DD”: 2000-JUL-01). Missing portions of dates should be represented on patient listings as missing (2000-JUL). Dates that are missing because they are not applicable for the patient are output as “N/A”, unless otherwise specified.
6. Time should be printed in SAS TIME5.format (“HH:MM”: 17:30). Missing portions of time should be represented on patient listings as dashes (--:30). Times that are missing because they are not applicable for the patient are output as “N/A”, unless otherwise specified.

8.2 Table of Contents for Tables, Listings and Figures

8.2.1 List of Tables

To be provided with TLF Shells

8.2.2 List of Listings

To be provided with TLF Shells

10.1 Table of Contents of Interim Analysis

Table 14.1.1.2 Summary of Patient Disposition	Full Analysis Set
Table 14.1.2 Summary of Demographic and Baseline Characteristics	Full Analysis Set
Table 14.1.3 Summary of Major Protocol Deviations	Full Analysis Set
Table 14.1.4 Summary of Prior Cancer Therapy	Full Analysis Set
Table 14.1.6 Summary of Concomitant Medication	Full Analysis Set
Table 14.1.7 Summary of Study Drug Exposure	Full Analysis Set
Table 14.2.1.1.1 Summary of Complete Response Rate Patients with CIS at Baseline	Full Analysis Set
Table 14.2.1.1.2 Summary of Detailed Response for Each Patient at Week 12.	Full Analysis Set
Table 14.2.1.2.1 Summary of Duration of Complete Response Patients with CIS at Baseline with Complete Response	Full Analysis Set
Table 14.2.1.2.2 Kaplan-Meier Estimate of Duration of Complete Response Patients with CIS at Baseline with Complete Response	Full Analysis Set
Table 14.2.2.1.1 Kaplan-Meier Estimate of Event-Free Survival	Full Analysis Set
Table 14.2.2.1.2 Sensitivity Analysis of Summary of Event-Free Survival – Binomial Method	Full Analysis Set
Table 14.2.2.2.1 Kaplan-Meier Estimate of Time to Recurrence	Full Analysis Set
Table 14.2.2.2.2 Sensitivity Analysis of Summary of Time to Recurrence – Binomial Method	Full Analysis Set
Table 14.3.1.1.2 Overall Summary of Treatment-Emergent Adverse Events - Patients with Baseline CIS	Full Analysis Set
Table 14.3.1.2.4 Summary of Treatment-Emergent Adverse Events by Preferred Term - Patients with Baseline CIS	Full Analysis Set
Table 14.3.1.5.4 Summary of Treatment Related Treatment-Emergent Adverse Events by Preferred Term - Patients with Baseline CIS	Full Analysis Set
Table 14.3.1.8.4 Summary of Serious Adverse Events by Preferred Term - Patients with Baseline CIS	Full Analysis Set
Table 14.3.1.9.4 Summary of Treatment Related Serious Adverse Events by Preferred Term - Patients with Baseline CIS	Full Analysis Set
Table 14.3.1.3.4 Summary of Treatment-Emergent Adverse Events by Preferred Term and Maximum Severity - Patients with Baseline CIS	Full Analysis Set
Table 14.3.1.12.4 Summary of Treatment Related Treatment-Emergent Adverse Events by Preferred Term and Grade - Patients with Baseline CIS	Full Analysis Set
Figure 14.2.1.2.1 Kaplan-Meier Plot for Duration of Response for Patients with CIS at Baseline with Complete Response	Full Analysis Set
Figure 14.2.1.2.2 Swim Lane Plot for Time to Complete Response and Duration of Response for Patients with CIS at Baseline with Complete Response	Full Analysis Set
Figure 14.2.2.1 Kaplan-Meier Plot for Event-Free Survival	Full Analysis Set
Figure 14.2.2.2 Kaplan-Meier Plot for Time to Recurrence	Full Analysis Set

This document is confidential.
